## **MATERIALS AND METHODS**

### ***Study Population and Protocol***

This was a single-center, prospective, assessor-blinded, noninferiority, randomized controlled study conducted at a tertiary referral center (Incheon St. Mary's Hospital, Incheon, Korea). Individuals who underwent colonoscopy with or without esophagogastroduodenoscopy (EGD) for various indications were eligible for inclusion. Study subjects were enrolled between November 2017 and February 2018. Individuals who met all of the following criteria were included: (1) age 40–75 years; (2) American Society of Anesthesiologists (ASA) class I or II; (3) outpatients; and (4) no previous history of bowel resection or gastrectomy. Exclusion criteria were as follows: (1) cancellation, (2) violation of protocol for bowel preparation, such as subjects in the SDD group ingesting a purgative the previous day or as an SPD; or subjects in the SPD group ingesting a purgative the previous day or as an SDD. After informed consent was obtained, study subjects were randomly assigned to the SDD or SPD group. Randomization was performed using a block size of four, stratified by colonoscopy time (morning vs afternoon) and sex, using a computer-generated randomization list.

The protocol for bowel preparation is shown in Figure 1. Subjects underwent bowel preparation at home. Study subjects were encouraged to finish 2 L PEG within 1 h. If ingestion was difficult, 2 L PEG was consumed within 1.5 h. Hence, 2 to 3 h were required to fully ingest the 4 L PEG. Individuals in the SDD group ingested PEG on the day of the colonoscopy. For those who underwent morning colonoscopy, ingestion of 4 L PEG was started at 5 a.m. Individuals who were scheduled to undergo afternoon colonoscopy were instructed to take 2 L PEG starting at 7 a.m., then after a 2-h break, the remaining 2 L PEG was ingested starting at 10 a.m. Individuals in the SPD were instructed to begin ingesting 2 L

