PEG at 9 p.m., 1 day before the colonoscopy. The remaining 2 L PEG was ingested from 7 a.m. for morning colonoscopy or from 10 a.m. for afternoon colonoscopy. We encouraged the participants to ingest additional water until their bowel effluent was clear. Consumption of fibers and seeds was restricted for 2 days before colonoscopy. Soft food was allowed for dinner the day before colonoscopy. Colonoscopy was performed between 10 a.m. and 5 p.m. (morning colonoscopy 10 a.m.–12 p.m.; afternoon colonoscopy 1:30 p.m.–5 p.m.) by three board-certified colonoscopists with experience of more than 2000 cases. The colonoscopists were blinded to the bowel cleansing regimen. This study was approved by the Institutional Review Board of Incheon St. Mary's Hospital and registered at ClinicalTrials.gov (NCT03315949).

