### ***Bowel Cleansing Efficacy, Bowel Movement Kinetics, and Colonoscopy Results***

The primary endpoint of this study was the bowel cleansing efficacy assessed by the Boston bowel preparation scale (BBPS). The BBPS score is the sum of three segmental scores (range 0–9). Each segment is graded on a 4-point scale: 0, inadequate; 1, poor; 2, good; and 3, excellent. The rates of cleansing success, defined as all segments  $\geq 2$  and total BBPS score, were compared between groups. The bowel cleansing efficacy was also assessed by the Aronchick scale, which has scores of excellent, good, fair, poor, and very poor; details of the Aronchick scale are described elsewhere.

Bowel movement kinetics included the number of defecations, the start and finish time of bowel preparation, and the last defecation time. The amount of PEG and additional water ingested were recorded.

The results of the colonoscopy were analyzed. The cecal intubation time, colonoscopy withdrawal time, polyp detection rate (PDR), ADR, and the number of adenomas per patient

were recorded. For those who underwent EGD, fluid in the stomach was suctioned and its volume was measured.

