### ***Statistical Analysis***

We assumed a bowel cleansing success rate for SPD of 85% and set the inferior margin at 10%. With 80% power and a type I error of 0.05, the required sample size for each group was calculated to be 158. A total of 176 subjects in each group was required, considering a 10% drop-out rate. Continuous variables are expressed as mean  $\pm$  standard deviation. Categorical variables are expressed as number and percent. The demographic characteristics, bowel cleansing efficacy, safety profile, tolerability, bowel movement kinetics, and results of colonoscopy were compared between the two groups. For this analysis, we used Student's *t* test for continuous variables, and the chi-square or Fisher's exact test for categorical variables. A *p*-value  $<0.05$  was considered significant. The safety analysis of safety and

tolerability included all subjects except those who were excluded for cancellation or protocol violation. Per-protocol (PP) analysis was used for the patients who completed colonoscopy. Bowel cleansing efficacy and bowel movement kinetics were investigated in the PP analysis. All statistical analyses were conducted using SAS software (9.0; SAS Institute, Cary, NC, USA).

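### Start, finish and last-defecation times are compared with a t test that ignores colonoscopy session; start time needs no test, and the other two should be compared within session (minor, free improvement)

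*Combined protocol and SAP*

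**What the plan says.** The section on bowel cleansing efficacy, kinetics and colonoscopy results lists the variables: "Bowel movement kinetics included the number of defecations, the start and finish time of bowel preparation, and the last defecation time". It adds "The amount of PEG and additional water ingested were recorded". It lists no interval from the end of preparation, or from the last defecation, to colonoscopy.

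Statistical Analysis includes kinetics among the domains tested: "bowel movement kinetics, and results of colonoscopy were compared between the two groups". For the method, "we used Student's *t* test for continuous variables", with p < 0.05 as the threshold. No stratification or adjustment is stated. The analysis set is also given: "Bowel cleansing efficacy and bowel movement kinetics were investigated in the PP analysis".

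Study Population and Protocol fixes the drinking times by arm and session.
- **Same-day arm (SDD), morning:** "For those who underwent morning colonoscopy, ingestion of 4 L PEG was started at 5 a.m".
- **SDD, afternoon:** the first 2 L starts at 7 a.m. and the second at 10 a.m.
- **Split arm (SPD):** the first 2 L starts at 9 p.m. the evening before; then "The remaining 2 L PEG was ingested from 7 a.m. for morning colonoscopy or from 10 a.m. for afternoon colonoscopy".

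The same section stratifies randomization by colonoscopy session and by sex, in blocks of four.

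**The concern.** Three of the four kinetics variables are times, and the plan puts them through a default two-sample test. This raises two problems.

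First, the regimen itself sets the start time. A test of it asks whether participants assigned to start in the evening started earlier than those assigned to start in the morning. The answer is known before any data arrive and says nothing about bowel response.

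Second, finish time depends strongly on whether the appointment is in the morning or the afternoon. A test that ignores session treats that gap as noise. The schedule also implies an arm difference in the morning only, and a single pooled comparison averages it with an afternoon difference of zero. A reader could then see a non-significant result and conclude that the regimens end at the same time, when the plan's own schedule says that in the morning they do not.

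What is at stake is the readability and precision of a secondary, descriptive domain.

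**Working it through.** **Inputs from the documents.** The drinking start times are as above. Pace is 1 to 1.5 h per 2 L, hence 2 to 3 h for 4 L. Colonoscopy runs 10 a.m. to 12 p.m. or 1:30 to 5 p.m. The sample size is 158 per group.

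**The plan's own figure.** With 85% success in both arms, a margin of 0.10, one-sided 0.05 and 80% power:

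n = (1.645 + 0.842)² × 2 × 0.85 × 0.15 / 0.10² = 157.7, so 158. Then 158 / 0.9 = 175.6, so 176.

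Both figures reproduce. The documents give no figure for kinetics; 158 per arm is used below.

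**Start time, SDD minus SPD.** Morning: 5 a.m. against 9 p.m. the day before, 8 h. Afternoon: 7 a.m. against 9 p.m., 10 h. Even with an assumed SD of 3 h, the SE is 3 × √(2/158) = 0.34 h, so an 8 h difference is about 24 standard errors. Power is effectively 1.

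**Scheduled finish time and its midpoint.**

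| Session | SDD | SPD | SDD minus SPD at equal pace |
|---|---|---|---|
| Morning | 7:00–8:00 (7:30) | 8:00–8:30 (8:15) | −1.0 to −0.5 h |
| Afternoon | 11:00–11:30 (11:15) | 11:00–11:30 (11:15) | 0 h |

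Within an arm the sessions lie about 3 h apart (SPD) or 3.5 to 4 h apart (SDD).

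**Precision of the finish-time comparison.** Three assumptions are not in the documents: half of each arm is examined in the morning, arm-by-session means sit at the schedule midpoints, and the within-session SD is 0.75 h (range 0.5 to 1.0 h). The average arm difference in size is 0.5 × 0.75 + 0.5 × 0 = 0.375 h.

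Pooled variance = within-session variance + (half the gap between session means)².
- SPD: 0.5625 + 1.5² = 2.8125, SD 1.68 h.
- SDD: 0.5625 + 1.875² = 4.078, SD 2.02 h.
- Unstratified SE = √[(2.8125 + 4.078)/158] = 0.209 h.
- Within-session SE, combined over sessions = √[2 × 0.5625/158] = 0.084 h.

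Approximate power for 0.375 h at two-sided 0.05 is Φ(0.375/SE − 1.96):
- Unstratified: Φ(1.80 − 1.96) = 43%.
- Within session: Φ(4.44 − 1.96) = 99%.

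The 43% is, if anything, generous, because it lets the session mix vary by chance between arms. If stratified randomization holds the mix equal, the difference varies with SD 0.084 h but must still exceed 1.96 × 0.209 = 0.409 h. The probability is then 1 − Φ[(0.409 − 0.375)/0.084] = 1 − Φ(0.40) = about 34%.

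**Sensitivity to the within-session SD.**

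| SD (h) | Unstratified SE (h) | Within-session SE (h) | Ratio |
|---|---|---|---|
| 0.5 | √[(2.5 + 3.766)/158] = 0.199 | 0.056 | 3.5 |
| 0.75 | 0.209 | 0.084 | 2.5 |
| 1.0 | √[(3.25 + 4.516)/158] = 0.222 | 0.113 | 2.0 |

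**Would an interval to colonoscopy do better?** With appointments spread evenly over the stated hours, their variance is 2²/12 = 0.333 (morning) and 3.5²/12 = 1.021 (afternoon), average 0.677. The within-session SE of the finish-to-colonoscopy interval is √[2 × (0.5625 + 0.677)/158] = 0.125 h, giving about 85% power. That is better than the unstratified test but worse than finish time compared within session. With appointment times balanced by randomization, the expected arm difference is the finish-time difference with its sign reversed.

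**The case against.** **Last defecation is not scheduled.** One might infer that the schedule fixes the arm difference in all three times. The documents support that for start time and largely for finish time. Last defecation is a participant outcome with no assigned time, so only the session-spread argument can reach it, and no size can be given.

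**The interval is not shown to be the better endpoint.** One might also infer that the plan measures the wrong thing, and that the gap before colonoscopy is what matters for cleansing. The documents do not say so, and do not state that colonoscopy start time was recorded. The interval's mean difference is as schedule-driven as that of finish time. The interval does carry patient-level information that clock time discards, since the windows are 2 h and 3.5 h wide, but that supports reporting it rather than replacing the listed variables.

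**No causal separation.** Comparing intervals between arms cannot distinguish an effect of the gap from an effect of same-day dosing, because the gap follows from regimen and session.

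**The recorded times have uses.** Participants who took the purgative on the wrong schedule are excluded, so actual start and finish times document adherence. The number of defecations is untouched by this point. The t-test sentence is a general default, the time scale is not stated, and the plan attaches no conclusion to a start-time p-value.

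All of this stands. It does not rescue the start-time test, or the omission of session from the finish and last-defecation comparisons.

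**Conclusion.** The point holds as a minor one. The start-time p-value is uninformative because the arms are assigned starts 8 to 10 h apart. For finish time, ignoring session inflates the standard error by a factor of about 3.5 to 2.0 for within-session SDs of 0.5 to 1.0 h. This assumes 158 per arm, an even morning and afternoon split, and finish times centred on the schedule; none of these is observed. Pooling also averages an expected morning difference of 0.5 to 1.0 h with an afternoon difference of zero. For last-defecation time the same loss is plausible but not calculable.

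The documents do not support the stronger readings that every kinetics contrast is fixed by design, or that leaving out the interval to colonoscopy prevents a cleansing difference from being explained. Nothing here touches the primary cleansing endpoint, the margin or the sample size.

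**What to change.** In Statistical Analysis:
1. Report preparation start time descriptively by arm and session, without a test, and state the time scale, since SPD starts fall on the previous day.
2. Compare finish time and last-defecation time between arms within colonoscopy session. Report both sessions, and combine them with a stratified estimate or a model adjusted for session.
3. If colonoscopy start time was recorded, add the intervals from end of preparation and from last defecation to colonoscopy, by arm and session, as descriptive secondary measures. Do not use them to claim a cause for any cleansing difference.
4. Do not add a test of first ingestion to last defecation. In the morning, scheduled drinking alone spans 11 to 11.5 h in SPD (9 p.m. to 8–8:30 a.m.) and 2 to 3 h in SDD, so that contrast is also largely set by the schedule.

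Items 1 and 2 change analysis wording only and use times already collected and a stratum already defined. The cost is the loss of three simple t tests. Item 3 depends on the sponsor confirming that colonoscopy start time is available. This is a free improvement of minor severity.

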### ***Safety and Tolerability***

The composite safety profile included vital signs and questionnaire findings. Vital signs were checked on the day of randomization and at colonoscopy. Before the colonoscopy, all study subjects completed a questionnaire asking about adverse events, tolerability, and bowel movement kinetics. The questionnaire contained the following items: (1) adverse events related to the ingestion of the purgative; (2) number of sleep disturbances during the night before colonoscopy; (3) overall satisfaction with the bowel cleansing regimen (very satisfied, satisfied, intermediate, dissatisfied, very dissatisfied); and (4) willingness to use the bowel preparation regimen again. The patients used a checklist of possible adverse events to report whether they had experienced any of the following during or after ingestion of the bowel cleanser: nausea, vomiting, bloating, abdominal pain, dizziness, headache, and/or any other symptoms.

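### Vital signs are read twice, but the plan does not say which value is compared and names no baseline-adjusted analysis, so precision is lost on a safety outcome

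*Combined protocol and SAP*

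**What the plan says.** The Safety and Tolerability section makes vital signs a named component of safety: "The composite safety profile included vital signs and questionnaire findings". It gives two measurement times: "Vital signs were checked on the day of randomization and at colonoscopy". Bowel preparation takes place at home after randomization, so the first reading can serve as a baseline.

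The Statistical Analysis section lists what is compared between arms: "bowel cleansing efficacy, safety profile, tolerability, bowel movement kinetics, and results of colonoscopy were compared between the two groups". For continuous variables it names Student's t, and the sentence runs "test for continuous variables, and the chi-square or Fisher's exact test for categorical variables". Results are to be shown as mean and standard deviation, with a p-value below 0.05 as the criterion. No confidence interval for a difference is mentioned, and no ANCOVA, repeated-measures model or other adjustment appears. Vital signs are not mentioned by name in that section, and the variable to be tested (colonoscopy value, each time point, or change) is not defined.

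The Study Population and Protocol section stratifies randomization by sex and by morning or afternoon colonoscopy. The analysis section does not use these factors.

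**The concern.** When an outcome is measured before and after an intervention, the first reading explains part of the between-subject spread in the second. A t test on the second reading ignores that information. A t test on the change uses it, but forces its coefficient to 1, which adds noise when the correlation is moderate. ANCOVA estimates the coefficient from the data.

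Two things are at stake. First, a wider interval makes a real difference between regimens easier to miss. With a significance criterion and no planned interval, a non-significant safety result is easily taken as reassurance. Second, because the analysed variable is undefined, the choice between final value and change could be made after both results are known.

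**Working it through.** **Inputs from the documents.** Two vital-sign readings per subject (Safety and Tolerability). From Statistical Analysis: an unadjusted t test for continuous variables, significance level 0.05, 85% assumed success with the split-dose (SPD) regimen, a 10% margin, 80% power, 158 per group, and 176 per group after 10% drop-out.

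**Inputs assumed.** The correlation r between the two readings is not given, so 0.3, 0.5 and 0.7 are used. Standard deviations are taken as equal at the two times and in the two arms. The vital-sign tests are taken as two-sided. The size of the safety set is not stated, so 158 per arm is used for illustration.

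**The plan's own figure.** The plan says "With 80% power and a type I error of 0.05, the required sample size for each group was calculated to be 158". With equal true rates:

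n = (z0.95 + z0.80)² × 2 × 0.85 × 0.15 / 0.10² = (1.645 + 0.842)² × 25.5 ≈ 157.7, rounded up to 158.

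This reproduces the figure with a one-sided 0.05; a one-sided 0.025 would give 201. Drop-out: 158 / 0.90 = 175.6, rounded up to 176. These figures concern the primary endpoint only. The plan states no precision or power for vital signs.

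**Relative variance of the treatment difference**, with a t test on the colonoscopy value set to 1:

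- t test on change: 2(1 − r)
- ANCOVA: 1 − r²
- ANCOVA relative to change: (1 − r²) / [2(1 − r)] = (1 + r)/2

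| r | Change | ANCOVA | Reduction vs colonoscopy value | Reduction vs change |
|---|---|---|---|---|
| 0.3 | 1.40 | 0.91 | 9% | 35% |
| 0.5 | 1.00 | 0.75 | 25% | 25% |
| 0.7 | 0.60 | 0.51 | 49% | 15% |

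The ordering does not depend on these values of r. ANCOVA beats the colonoscopy-value test by r², and beats the change test by 2(1 − r) − (1 − r²) = (1 − r)². Both are positive for any r between 0 and 1. At r = 0 ANCOVA gains nothing over the colonoscopy-value test.

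**Effective sample size.** Against the colonoscopy-value test, 158/(1 − r²) gives 174, 211 and 310 per arm at r = 0.3, 0.5 and 0.7.

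**Difference detectable with 80% power**, two-sided 0.05, 158 per arm. On the colonoscopy value it is (1.960 + 0.842) × √(2/158) = 0.315 SD. The other methods multiply this by the square root of the relative variance. Power is for an illustrative true difference of 0.3 SD; the documents name no relevant difference.

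| r | Detectable (SD): colonoscopy value / change / ANCOVA | Power at 0.3 SD: colonoscopy value / change / ANCOVA |
|---|---|---|
| 0.3 | 0.315 / 0.373 / 0.301 | 76% / 62% / 80% |
| 0.5 | 0.315 / 0.315 / 0.273 | 76% / 76% / 87% |
| 0.7 | 0.315 / 0.244 / 0.225 | 76% / 93% / 96% |

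**The case against.** A reader might infer that the plan throws the first reading away. The documents do not support that. A t test on change would use it and fits the text as well as a t test on the colonoscopy value. What stands is that the variable is undefined and that no baseline-adjusted model is named. The precision argument survives because ANCOVA does better on both readings.

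A reader might also infer bias from an uncorrected chance imbalance at baseline. That does not follow. Allocation is randomized, so either t test is unbiased, and its standard error already allows for chance imbalance.

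Nor do the documents support a clinical reading in which fluid loss shows up as blood-pressure or heart-rate differences between arms. They do not name those signs or predict such a difference, and both arms take 4 L. They also give vital signs no particular weight within the safety profile.

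The size of the gain rests on an assumed r, and part of the range is modest: at r = 0.3 the detectable difference falls only from 0.315 to 0.301 SD against the colonoscopy value. This objection stands and limits the weight of the point. It does not remove it, since the same r gives a 35% variance reduction against the change test.

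Finally, the text is in the past tense and reports enrolment between November 2017 and February 2018. Adjustment added now may not be prespecified. That stands too, and affects how the analysis is labelled.

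**Conclusion.** The point holds as a minor, worthwhile improvement. The plan collects two vital-sign readings, does not define the variable compared, and names only an unadjusted t test. For any correlation between 0 and 1 with equal standard deviations, ANCOVA is more precise than either version of that test. At correlations of 0.3 to 0.7 the variance reduction is 9% to 49% against the colonoscopy value and 35% to 15% against change. The direction is secure; the size is not, because the documents give neither the correlation nor a standard deviation.

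The consequence is confined to precision on a non-primary safety outcome. The Boston scale endpoint, the 10% margin and the 158 and 176 per group are unaffected.

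**What to change.** Add one sentence to Statistical Analysis: each vital sign at colonoscopy is analysed by ANCOVA with arm, the randomization-day value, colonoscopy time (morning or afternoon) and sex, and the adjusted difference between arms is reported with its 95% confidence interval. This also settles which variable is analysed.

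The cost is small. The readings and stratification factors are already recorded, no extra subjects are needed, and the few degrees of freedom spent are negligible at about 158 per arm. If the sentence is added after the data were seen, label the analysis post hoc and show the unadjusted comparison beside it.

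### Adverse events are collected only before the colonoscopy, so the safety comparison covers essentially only the period before the examination

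*Combined protocol and SAP*

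**What the plan says.** Safety and Tolerability names two components: "The composite safety profile included vital signs and questionnaire findings". On the first, "Vital signs were checked on the day of randomization and at colonoscopy". On the second, "Before the colonoscopy, all study subjects completed a questionnaire asking about adverse events, tolerability, and bowel movement kinetics". The adverse-event item asks about "adverse events related to the ingestion of the purgative", and the checklist asks whether subjects "experienced any of the following during or after ingestion of the bowel cleanser". That checklist wording has no end point of its own, but the form is completed before the examination starts.

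The section on cleansing efficacy, kinetics and colonoscopy results lists what is recorded at the examination: insertion and withdrawal times, polyp and adenoma detection, and adenoma counts. It adds: "For those who underwent EGD, fluid in the stomach was suctioned and its volume was measured". EGD was optional ("Individuals who underwent colonoscopy with or without esophagogastroduodenoscopy (EGD) for various indications were eligible for inclusion"), so gastric volume exists for a subset only, and it is listed with the examination results, outside the safety profile. The same section records when preparation started and finished, and how much PEG and extra water was drunk.

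Statistical Analysis compares the safety profile between the groups and names no further source of safety data.

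**The concern.** The two regimens differ in how the PEG is spread over time, and subjects in both arms may drink more: "We encouraged the participants to ingest additional water until their bowel effluent was clear". The investigators thought stomach contents worth measuring, yet nothing they planned to collect lets that volume be read against a clinical event. A subject who is well when filling in the form and then vomits, desaturates or has the examination stopped for a safety reason has no adverse-event field in which this would appear.

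At stake is the scope of the safety conclusion. A statement that the regimens have similar safety, made without qualification, would be read as covering the examination and recovery. The data described cover the time up to the questionnaire, plus whatever a vital-sign reading of unknown timing happens to show. An excess of events in either arm after that point could go unseen.

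**Working it through.** **Step 1. Trace each safety source to the time it covers.**

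| Source | Section | Window covered |
|---|---|---|
| Questionnaire, adverse-event item | Safety and Tolerability | Up to completion, before the examination; purgative-related events only |
| Vital signs, first set | Safety and Tolerability | Day of randomization |
| Vital signs, second set | Safety and Tolerability | At colonoscopy; before, during or after insertion not stated |
| Gastric fluid volume | Colonoscopy results | During EGD, subset only; a volume, not an event, and outside the safety profile |
| Other examination data | Colonoscopy results | During the examination; no complication item |
| Recovery or later contact | None described | Not covered |

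An event first arising during the examination could show only through the second set of vital signs, if these were taken at the right moment. An event first arising in recovery has no described route at all.

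**Step 2. Check whether the schedule predicts a direction.** Inputs are from Study Population and Protocol: 1 to 1.5 h per 2 L, so 2 to 3 h for 4 L; morning examinations from 10 a.m., afternoon ones from 1:30 p.m.

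| Session | SDD: last PEG finished | SPD: last PEG finished |
|---|---|---|
| Morning | 5 a.m. + 2 to 3 h = 7 to 8 a.m. | 7 a.m. + 1 to 1.5 h = 8 to 8:30 a.m. |
| Afternoon | 10 a.m. + 1 to 1.5 h = 11 to 11:30 a.m. | 10 a.m. + 1 to 1.5 h = 11 to 11:30 a.m. |

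For the earliest morning slot the gap to the examination is 2 to 3 h for SDD and 1.5 to 2 h for SPD. For the earliest afternoon slot it is 2 to 2.5 h in both arms. SDD subjects drink 4 L on the day against 2 L, but they finish no later. The documents predict no direction.

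**Step 3. What the trial's size could say if events were captured.** The planned size reproduces. With 85% success in both arms, a 10-point margin, one-sided alpha 0.05 and 80% power, n = 2 × 0.85 × 0.15 × (1.645 + 0.842)² / 0.10² = 157.7, rounded up to 158. Allowing for drop-out, 158 / 0.9 = 175.6, rounded up to 176. The plan does not state whether alpha is one- or two-sided; one-sided 0.025 would give 201, so 158 corresponds to one-sided 0.05.

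With zero events in n subjects, the exact one-sided 95% upper bound is 1 − 0.05^(1/n). This is 1.9% for n = 158 and 1.7% for n = 176.

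The documents give no peri-procedural event rate, so the rates below are assumptions spanning a range. For one arm of 158, the expected count is 158p and the chance of at least one event is 1 − (1 − p)^158.

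| Assumed rate p | Expected events | Chance of at least one |
|---|---|---|
| 0.1% | 0.16 | 15% |
| 0.5% | 0.8 | 55% |
| 1% | 1.6 | 80% |
| 2% | 3.2 | 96% |

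Counts this small can be described but give no useful power for a comparison between arms.

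**The case against.** The best case against the point has four parts.

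- **Mechanism.** A reader might infer that drinking 4 L on the day exposes SDD subjects to more risk at the examination, so that the window misses the period that matters most for that arm. The documents do not support this: the finishing times in Step 2 show SDD ending at the same time or earlier. Aspiration, regurgitation and sedation are not mentioned in the documents, so the link from gastric volume to harm is a clinical inference. This objection stands. It removes the presumed direction but leaves the gap in capture.
- **Time of last intake.** A reader might infer that nothing is known about when drinking stopped. In fact the finish time of preparation and the amount of extra water are both recorded. Only a clock time for water taken after preparation is not listed. This objection also stands.
- **Absolute wording.** It would be too strong to say that no event during the examination can reach the safety profile. Vital signs at colonoscopy might reflect one, and whether they include oxygen saturation is not stated. Completion of colonoscopy must also be known, because it defines the per-protocol set, so a stopped procedure is not wholly invisible, though its reason is not a listed item. The list of safety components may also not be meant as exhaustive. This narrows the point for events during the examination; none of it reaches events in recovery.
- **Scope.** The trial's primary endpoint is cleansing, its subjects are ASA I or II outpatients, and its adverse-event item is deliberately about the purgative. It states no safety margin and does not itself claim that the regimens are equally safe. That is fair and keeps the point modest. Even so, the plan does compare a safety profile between groups, and the reader of that comparison needs to know when it stops.

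**Conclusion.** The point holds as one about completeness. Following the plan as written leaves adverse events that first arise during the examination or in recovery without an event field in the between-group comparison. The only partial exception is the vital signs of unspecified timing. Neither the primary endpoint nor the sample size is affected.

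The documents do not support a claim that SDD carries the greater unseen risk, or that the trial has drawn an unsupported safety conclusion. The gain from closing the gap is an upper bound of just under 2% per arm if no events are seen, or a short descriptive list if some are. The verdict assumes that the sections supplied describe all safety data collection.

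**What to change.** Extend the safety outcome through discharge from the endoscopy unit:

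1. Transcribe from the procedure and recovery record any vomiting or regurgitation, suspected aspiration, oxygen desaturation, or procedure stopped for a safety reason. This assumes such a record exists; the documents do not describe one, so it needs to be checked.
2. Report these events by randomised group as counts and proportions with confidence intervals, labelled descriptive.
3. State when the vital signs at colonoscopy are taken relative to the examination, and which ones.
4. For EGD patients, report gastric volume against the interval from the recorded finish of preparation to the examination.
5. If the events cannot be obtained, say in the methods and conclusions that safety was assessed only for the period before the examination.

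The cost is a few data fields per subject and slight extra data entry, with no added visit, staff or procedure. The drawback is that few events are to be expected, so the result will not be a powered comparison.
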